## 13.2 Transfusion Therapy During Study Drug Administration

Subjects will receive 10-15 ml/kg/transfusion, with all volumes recorded on the Case Report Forms.

**13.2.1 If the hemoglobin (Hb) is less than 8 gm/dL and there is no evidence of reticulocyte response (retic count < 0.5%), the subject will be transfused as usual.**

**13.2.2 If the Hb is greater than 8 gm/dL, the reticulocyte count is greater than 0.5% (or baseline) and the subject is clinically stable (without fever, respiratory illness, etc.), the transfusion should be held.** The subject should be followed again in 1-2 weeks and reassessment will be made to see if a response is occurring.

**13.2.3 If the Hb is between 7-8 gm/dL, the reticulocyte count is greater than 0.5% (or baseline), and the subject is clinically stable, then the subject can opt out of transfusion, based upon clinical considerations, for one week, or receive 10 ml/kg packed red blood cell transfusion so as not to**

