## 14.0 EVALUATION CRITERIA

### 14.1 On-Study Response Criteria - evaluated at 6 and 9 months of treatment

#### 14.1.1 Complete Response (CR) – Hb $> 9$ gm/dL and weaned off of transfusion therapy

1a- Complete response lasting  $\geq 6$  months

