# Master Protocol

**14.1.2 Partial Response (PR)** - Hb < 9 gm/dL with an increase in reticulocyte count to 1% and any transfusion interval increase

**14.1.3 No Response (NR)** - No change in transfusion needs, no change in Hb or reticulocyte count

**14.1.4 Progression** - An increased transfusion requirement with increased volume or increased interval

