### 16.2 Specific Statistical Aims of the Study (for the Data Analysis)

**16.2.1** The primary objective of the study is to estimate the proportion of complete responders, partial responders or non-responders at 9 months. These proportions will also be estimated at 6 months.

**16.2.2** To determine the time-to-first occurrence of a CR or PR. Subjects who do not achieve CR or PR by the end of the study at 9 months will be considered 'censored for CR (PR)'.

**16.2.3** To catalogue the phenotypic characteristics of the responders and non-responders at 6 and 9 months.

**16.2.4** To examine the frequency and severity of adverse events (AEs) that may arise from the study and to determine if these AEs are related to the study drug.

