# Master Protocol

- a. Complete response (CR): Hb > 9 gm/dL and transfusion-independence as defined in DBA
- b. Partial response (PR): Hb < 9 gm/dL and increased reticulocyte count to greater than 1% and any increase in transfusion interval from baseline. (Baseline reticulocytes range from 0.1 to 0.5 and transfusions are usually performed every 3 weeks. An increase of reticulocyte counts to over 1 to 1.5% and any increase in transfusion interval will be considered a PR.)
- c. No response (NR): no change in transfusion requirements and no significant change in Hb or reticulocytes (or any response that does not satisfy the conditions of either a PR or CR)
- d. Progression: worsening of disease as defined by the need for more frequent transfusions

Secondary outcomes include time-to-occurrence of either a PR or CR, and safety parameters such as type, frequency, and severity of adverse events and relationship to leucine (according to the NCI CTCAE version 4.0).

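### Partial response accepts a longer transfusion interval of any size or duration, so one 1–2 week hold can complete it; time to first PR is most exposed, and PR overlaps with Progression

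*Combined protocol and SAP*

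**What the plan says.** **PR.** Section 14.1.2 defines it as "Hb < 9 gm/dL with an increase in reticulocyte count to 1% and any transfusion interval increase". Section 16.3b makes baseline the reference and adds that, together with a reticulocyte rise, "any increase in transfusion interval will be considered a PR". It describes the starting point only in general terms: "Baseline reticulocytes range from 0.1 to 0.5 and transfusions are usually performed every 3 weeks". Only complete response (CR) has a duration subcategory, of at least 6 months; PR has none.

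**Holds.** Section 13.2.2 says a transfusion should be held "If the Hb is greater than 8 gm/dL, the reticulocyte count is greater than 0.5% (or baseline) and the subject is clinically stable", with reassessment 1–2 weeks later. Section 13.2.3 returns a subject who does not go on responding to the usual schedule.

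**Timing.** Section 14.1 is headed "On-Study Response Criteria - evaluated at 6 and 9 months of treatment". The aim in 16.2.2 is different: "To determine the time-to-first occurrence of a CR or PR". Section 16.4 analyses this by Kaplan-Meier, separately for CR and PR.

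**Progression.** Section 14.1.4: "An increased transfusion requirement with increased volume or increased interval". Section 16.3d: "worsening of disease as defined by the need for more frequent transfusions".

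**The concern.** The interval part of PR can be produced by a single application of the protocol's own hold rule. Nothing in 14.1.2 or 16.3b says whether the latest, longest or mean interval is compared, how an interval still open is treated, or whether a lengthening that is later reversed still counts. A brief hold and a lasting fall in transfusion need can therefore receive the same label.

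PR is one of the four categories of the primary outcome in a single-arm, open-label trial, and section 16.5 expects the results to help set the effect size for Phase III. A PR proportion that mixes the two is a poor guide to the effect on transfusion burden. In addition, if a longer interval can belong to both PR and Progression, the four categories are not mutually exclusive and their proportions are not well defined.

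**Working it through.** **The plan's own figure.** Section 16.5 gives a maximum 95% half-width for n = 50: 1.96 × √(0.5 × 0.5 / 50) = 0.1386, or 13.9 points (36.1% to 63.9%). It reproduces. The issue here is what the PR proportion measures, not this precision.

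**Can one hold complete a PR?** Take a clinically stable subject with Hb 8.5 and reticulocytes 1.6%.
- 13.2.2: Hb above 8 and reticulocytes above 0.5%, so the transfusion is held.
- 14.1.2 and 16.3b: Hb below 9, and reticulocytes above 1% (above 1.5% on the strictest reading of 16.3b), so both laboratory parts are met.
- Interval: on the usual 21-day cycle a hold of 7 or 14 days gives 28 or 35 days (+33% or +67%), which is an increase.

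All three parts are met after one hold.

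**What one hold is worth in blood.** Inputs: 21-day spacing (16.3b), 28-day spacing (upper end of the 3–4 weeks in 12.2.3), holds of 7 or 14 days (13.2.2), constant volume. The reference is 84 days, the averaging period in 9.1.1.1, which is four 21-day or three 28-day cycles. One hold stretches those cycles to 91 or 98 days:
- 7-day hold: 84/91 − 1 = −7.7%
- 14-day hold: 84/98 − 1 = −14.3%
- lasting move from 21 to 28 days: 21/28 − 1 = −25%. At 10 ml/kg this is 10 × 28/21 = 13.3 falling to 10.0 ml/kg per 28 days.

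PR as written does not distinguish these.

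**Would averaging cure it?** Four 21-day intervals with one hold have a mean of (84 + 7)/4 = 22.75 days or (84 + 14)/4 = 24.5 days. Both exceed 21, so a mean with no minimum change still scores the single hold as an increase.

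**Where the exposure lies.** At the 6- and 9-month assessments, a subject who held once early and then went back to schedule can be scored as no response, although no look-back window is stated. Time to first PR is recorded at its first occurrence, with no confirmation rule and no list of scoring visits, so a later reversal does not undo it.

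**PR against Progression.** Section 13.2 allows 10–15 ml/kg. Take the two ends: 10 ml/kg every 3 weeks is 13.3 ml/kg per 28 days; 15 ml/kg every 4 weeks is 15.0. The change is 15.0/13.33 − 1 = +12.5%. Requirement, volume and interval have all increased, so 14.1.4 is met. With the laboratory parts met, so is 14.1.2. Under 16.3d it is not Progression, because transfusions are less frequent. Any volume above 13.3 ml/kg at 4 weeks has the same effect against that baseline.

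**The case against.** The strongest defence is that PR is not an interval measure alone. Reticulocytes must reach about 1% against a stated baseline of 0.1–0.5%, which is separate evidence of red cell production and a higher bar than the 0.5% hold trigger. A reader might infer that every hold becomes a PR. The documents do not support that: a hold at reticulocytes between 0.5% and 1%, or at Hb above 9, does not meet PR at that time.

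The protocol also treats a hold as a test, with reassessment and a return to schedule if the response does not continue. That is right as patient management, but the result of the test is never carried into the PR definition.

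The objective is haematologic response, the analysis is mainly descriptive, the sample is one of convenience, and no decision rule depends on PR. On-study dates and volumes are recorded, so intervals can be re-scored. All of this stands and limits the severity.

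A reader might also want a figure for the inflation of time to first PR. The documents give neither the chance of a transient PR reading nor the scoring visits, and the only evaluation times they state for response are 6 and 9 months. Any such figure would come from its assumptions.

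Nor should 9.1.2, where the subject stays on the transfusion schedule, be read as forbidding holds. Its context is concurrent DBA treatment, and that reading would also rule out CR.

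On Progression, the longer interval in 14.1.4 may be a wording slip, as 16.3d suggests. It is still the current text.

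**Conclusion.** The concern holds in a limited form. As written, one 1–2 week hold in a stable subject with Hb between 8 and 9 and reticulocytes above 1% can complete a PR and is scored the same as a lasting lengthening, although the change in blood use is 7.7–14.3% against 25%. Those percentages assume constant volume and regular 21- or 28-day spacing.

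The effect is confined to PR, since CR is reported separately. It is limited for the 6- and 9-month proportions and greatest for time to first PR. A reader might infer that the primary PR proportion is materially inflated; the documents give no basis for saying so, or for sizing it.

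The conflict between 14.1.4 and 16.3d does not depend on any of these assumptions. The +12.5% example does use the ends of the permitted volume range. Both matters should be settled before analysis; neither undermines the trial.

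**What to change.** 1. **Keep PR and add a burden measure.** Report beside it the paired within-subject change in transfused volume per kg per 28 days (units above 60 kg, as in 9.1.1.1), for the 84 days before the 6- and 9-month assessments against the 84 days before entry. Use a 95% CI suited to skewed data, such as a bootstrap, because transfusion-free subjects score −100%, and make no advance claim of precision. Treat it as a group measure: in one subject the 84-day count moves in steps of 25% (4 to 3 transfusions) or 33% (3 to 2), and a single hold can cause a full step.
2. **Define and confirm.** State which interval is scored for PR and at which visits time to first PR is scored. As a sensitivity analysis, count PR at 6 and 9 months, and time to first PR, only when both the longer interval and the reticulocyte criterion are confirmed. One option is two consecutive intervals longer than the subject's pre-entry mean, with the reticulocyte criterion met at two consecutive visits. Give rules for an interval still open at the assessment and for a first PR at month 9, which has no later scheduled visit.
3. **Reconcile** 14.1.2, 14.1.4, 16.3b and 16.3d so that PR and Progression are mutually exclusive. How they are reconciled is for the sponsor; no transfusion rule is proposed here.

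**Cost.** Mostly wording. On-study dates and volumes are already collected (12.2.3, 13.2). Section 9.0 requires eligibility data to be in the subject's record, but 12.1.4 lists only a transfusion history, so pre-entry dates and volumes may need abstracting for up to 50 subjects. The confirmed PR rate may be lower than the rate as defined.

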# Master Protocol

abort a possible response. If the subject continues to show a response then Hb can be checked every 2 weeks and transfusion held. If not, the subject will resume the transfusion schedule.

## 13.3 Schedule of Evaluations

Oral Leucine x 9 months

VISIT *	0	2wk	4wk	2mo	3mo	4mo	5mo	6mo	7mo	8mo	9mo
PE **	X	X	X	X	X	X	X	X	X	X	X
BP	X	X	X	X	X	X	X	X	X	X	X
Height	X					X					X
Weight	X	X	X	X	X	X	X	X	X	X	X
CBC with Retic ***	X	X	X	X	X	X	X	X	X	X	X
%Hb F	X				X			X			X
Chemistry**** Panel	X	X	X	X	X	X	X	X	X	X	X
Ferritin	X				X			X			X
Pregnancy test	X				X			X			
Leucine level	X	X	X		X			X			X

\*Each visit can be  $\pm$  1 week of the requested time – except visit 2.

\*\* PE includes Temperature, Pulse and Blood Pressure complete physical exam as clinically necessary \*\*\* CBC to include WBC, RBC, Hb, Hct, Plts, differential and reticulocyte count (%)

\*\*\*\* Chemistry Panel to include Urea Nitrogen, Creatinine, AST, ALT, Bilirubin, total and direct,

## 13.4 Grading of Adverse Events

Adverse events (toxicities) will be graded according to the NCI Common Terminology Criteria for Adverse Events v4.0 (CTCAE) (<http://ctep.cancer.gov/reporting/ctc.html>). Any suspected or confirmed dose-limiting toxicity should be reported immediately (within 24 hours) to the Study PI.

## 13.5 Dose Modifications for Adverse Events

### 13.5.1 Dose Reduction

There will be no drug reduction for the study drug.

### 13.5.2 Dose Escalation

There will be no drug escalation for the study drug.

### 13.5.3 Dose Discontinuation

In the event of any serious adverse event (SAE), the study drug will be discontinued until all symptoms resolve. If the SAE is deemed possibly related to the protocol therapy, the subject will be removed from the study and leucine will be permanently discontinued.

## 14.0 EVALUATION CRITERIA

### 14.1 On-Study Response Criteria - evaluated at 6 and 9 months of treatment

#### 14.1.1 Complete Response (CR) – Hb $> 9$ gm/dL and weaned off of transfusion therapy

1a- Complete response lasting  $\geq 6$  months

# Master Protocol

**14.1.2 Partial Response (PR)** - Hb < 9 gm/dL with an increase in reticulocyte count to 1% and any transfusion interval increase

**14.1.3 No Response (NR)** - No change in transfusion needs, no change in Hb or reticulocyte count

**14.1.4 Progression** - An increased transfusion requirement with increased volume or increased interval

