### 16.3 Endpoint Variables

The primary outcome is the type of response observed at 9 months (and 6 months). Response to treatment can be one of the following:

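### Sections 14.1 and 16.3 define the primary response outcome in conflicting terms, and nothing in the available text says which one governs

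*Combined protocol and SAP*

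**What the plan says.** Section 16.3 names the type of response at 9 months (and 6 months) as the primary outcome and introduces its list with "Response to treatment can be one of the following". Section 14.1 sets on-study response criteria for the same two time points. Neither section cites the other.

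- **Complete Response (CR).** 16.3a: "Hb > 9 gm/dL and transfusion-independence as defined in DBA". Section 14.1.1 likewise needs Hb above 9 in a subject no longer on transfusion.
- **Partial Response (PR).** 14.1.2: "Hb < 9 gm/dL with an increase in reticulocyte count to 1% and any transfusion interval increase". 16.3b: "Hb < 9 gm/dL and increased reticulocyte count to greater than 1% and any increase in transfusion interval from baseline", followed by a note: "An increase of reticulocyte counts to over 1 to 1.5% and any increase in transfusion interval will be considered a PR".
- **No Response (NR).** 14.1.3 requires that transfusion needs, Hb and reticulocytes are all unchanged. 16.3c adds a catch-all: "or any response that does not satisfy the conditions of either a PR or CR".
- **Progression.** 14.1.4: "An increased transfusion requirement with increased volume or increased interval". 16.3d: "worsening of disease as defined by the need for more frequent transfusions".

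Sections 16.0, 16.3 and 16.4 use all four categories; 16.2.1 names only the first three. Section 16.4 reports a proportion with a 95% confidence interval for each of the four.

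**The concern.** Both lists apply to the same assessments, so a subject's primary-outcome category can depend on which section the assessor opens. The CR and PR labels also feed the time-to-response and phenotype analyses in 16.4, and section 16.5 says the results may help to set the effect size for a later Phase III trial. The study is open-label. If the choice between definitions is left until the data have been seen, it can be influenced by them.

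**Working it through.** **The plan's own precision figure.** Inputs from 16.5: n = 50, two-sided 95%, normal approximation, p = 0.5.

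Half-width = 1.96 × √(0.5 × 0.5 / 50) = 0.139, giving 36.1% to 63.9%. This agrees with the plan.

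**Volume conversion.** ml/kg per 28 days = ml/kg per transfusion × 28 / interval in days. The assumed baseline is 10 ml/kg (bottom of the 10-15 range in 13.2) every 21 days (the usual interval in 16.3b), with reticulocytes 0.4% (within the 0.1 to 0.5 of 16.3b): 10 × 28 / 21 = 13.3.

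**Test subjects under each section.** The profiles are hypothetical and the 16.3 column uses the main text of 16.3b.

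| Subject at assessment | ml/kg per 28 days | 14.1 | 16.3 |
|---|---|---|---|
| A. 15 ml/kg every 21 days, Hb 7.5, reticulocytes 0.4% | 15 × 28 / 21 = 20.0 | Progression, if the rise is an increased requirement | NR |
| B. 10 ml/kg every 28 days, Hb 8.5, reticulocytes exactly 1.0% | 10 × 28 / 28 = 10.0 | PR | NR |
| C. 10 ml/kg every 42 days, Hb 9.3, reticulocytes 1.6% | 10 × 28 / 42 = 6.7 | no category | NR |
| D. Off transfusion, Hb exactly 9 | 0 | no category | NR |
| E. 15 ml/kg every 28 days, Hb 8.5, reticulocytes 1.6% | 15 × 28 / 28 = 15.0 | PR, and also Progression if volume is counted per 28 days | PR |

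- **A, volume.** 14.1.4 counts volume without giving a basis; 16.3d does not mention it. The rise stays within the range allowed in 13.2.
- **Interval direction.** A longer interval at unchanged volume lowers the requirement, so the interval wording in 14.1.4 contradicts the opening of its own sentence. It also contradicts 16.3d and both PR definitions, where a longer interval is improvement.
- **B, reticulocyte cut-off.** The main texts of 14.1.2 and 16.3b differ only at exactly 1%. Within 16.3b, a subject at 1.2% meets the main text but fails the note if its upper figure of 1.5% is the cut-off. Declaring that 16.3 governs would not settle this.
- **C, improved but still transfused.** Hb of 9 or more rules out the main PR text and continued transfusion rules out CR, so 16.3c applies. The 16.3b note does not repeat the Hb condition, which makes PR arguable but no more. Section 14.1 has no category unless volume also rises.
- **D.** Hb of exactly 9 meets neither CR nor the main PR text in either section.

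**Effect on the reported proportions.** One subject is 1/50 = 2 points. Section 5.2 reports response rates of about 10% (IL-3, and later metoclopramide studies) and 33% (one metoclopramide study), used here only as an assumed range:

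- at 10%: 1.96 × √(0.10 × 0.90 / 50) = 8.3 points; one subject is 1 of 5 responders
- at 33%: 1.96 × √(0.33 × 0.67 / 50) = 13.0 points; one subject is 1 of about 16.5 responders

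**The case against.** The strongest reply is that the analysis definition stands in one place. Section 16.3 sits in the statistical chapter, is headed as the endpoint variables, and is exhaustive on its own because of its catch-all. The gaps in 14.1 therefore need not leave anyone unclassified in the analysis. This largely stands, but placement is an inference rather than a precedence rule, and it does not cure the reticulocyte inconsistency inside 16.3b.

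A reader might infer that 14.1.4 would score a longer interval, a sign of improvement, as Progression. The text does not support that: an increased requirement is needed first, and 18.4.4 also speaks of more frequent transfusion. The wording needs correcting, but it is a slip.

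A reader might also infer that Progression is dropped from the primary analysis because 16.2.1 lists three categories, or that it overlaps with NR because it is neither CR nor PR. Sections 16.0, 16.3 and 16.4 all list four, and the introduction to 16.3 points to a single category per subject. This is a minor matter of wording.

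Subject A is conditional: whether a rise within the permitted range is an increased requirement is not stated. Subjects B, C and E are less likely at a transfusion visit, because 13.2.2 holds transfusion in stable subjects with Hb above 8 and reticulocytes above 0.5% or baseline. That rule does not reach subject A.

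Finally, the appendices, including the Case Report Form (Appendix G), are not in the available text and may carry scoring instructions.

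**Conclusion.** The concern holds as a conflict of wording in the primary outcome that should be fixed. Three things survive a reading favourable to the plan: whether volume counts towards Progression, which reticulocyte cut-off defines PR, and where Hb of 9 or more while still transfused, and Hb of exactly 9, belong.

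The size is 2 points per reclassified subject, against half-widths of 8.3 to 13.0 points at assumed response rates of 10% to 33%, and 13.9 at most. How many subjects would be affected cannot be found from the documents. Counting hypothetical profiles on which the sections disagree would not tell us, since the count depends on the profiles chosen.

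The documents do not support the stronger conclusion that the primary outcome cannot be scored. The analysis is primarily descriptive, no decision threshold rests on these proportions, and a consistent derivation is possible if the rule is fixed first. The conclusion assumes that no precedence or scoring rule stands in the unavailable appendices.

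**What to change.** Before any response is scored, reconcile 14.1, 16.2.1 and 16.3 into one mutually exclusive and exhaustive set:

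- Correct the interval direction in 14.1.4 to agree with 16.3d.
- State whether volume counts towards Progression and on what basis. Section 9.1.1.1 already uses a per-28-day basis for eligibility.
- Give one reticulocyte cut-off for PR, and remove the second figure or explain it.
- Assign a category to Hb of 9 or more while still transfused, and to Hb of exactly 9.
- State which category prevails when the interval lengthens but volume per 28 days rises (subject E).
- Define NR as whatever remains after CR, PR and Progression, and name all four categories in 16.2.1.

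The clinical thresholds are for the sponsor to choose; none is proposed here. The cost is a wording amendment, with the Case Report Form checked for consistency. No new data are needed: sections 12.2 and 13.2 already collect Hb, reticulocytes, and transfusion dates and volumes.

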## 15.0 WITHDRAWAL AND OFF STUDY CRITERIA

**15.1 Subject's choice:** A subject may withdraw from the study at any time. The risk of withdrawing will be discussed, as will alternative treatment options. Once off study, subjects will be referred back to his or her referring physician. Alternative treatment will then be discussed with the primary hematologist.

**15.2 PI Decision:** Alternative treatment options will be discussed with the subject, who will then be referred back to his or her referring physician.

**15.3 Discontinuation for Toxicity:** Subjects will be discontinued from study for any Grade III/IV toxicity related to the study drug as determined by PI.

**15.4 Discontinuation for Non-Adherence:** Subjects will be discontinued from study if non-adherent to protocol.

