### **12.2.2 Laboratory Examinations**

**12.2.2.1** CBC with platelet count, differential, and red cell indices

**12.2.2.2** Reticulocyte count

**12.2.2.3** Percent Hemoglobin F at baseline and then every 3 months and at study completion

**12.2.2.4** Hepatic transaminases, serum bilirubin, creatinine, and blood urea nitrogen

**12.2.2.5** Serum ferritin at baseline and then every three months and at study completion

**12.2.2.6** If female and of child-bearing potential, pregnancy test at baseline and every 3 months

**12.2.2.7** Plasma leucine level as well as levels of isoleucine and valine and an amino acid profile at baseline. Plasma leucine levels are obtained for research only and will not be used for clinical decision making. This extra blood will be drawn at the same time as standard routine clinical blood draws. A standard 10cc's (2 teaspoons) will be taken as part of clinical care, with an additional 5 cc's (1 teaspoon) taken after Leucine treatment begins to monitor leucine levels in the blood. Plasma leucine levels (5 cc's) will also be drawn at 2 weeks, 4 weeks, then months 3, 6, and 9 months (These are the extra tests for this study protocol. All the others are standard of care for the enrolled subjects.) Subjects will fast for 4 hours and hold the morning dose of Leucine for evaluation of the Leucine level at these time points. Blood drawings can be  $\pm$  7 days of the requested time, except week 2.

Laboratory examinations 12.2.2.1, 12.2.2.2, 12.2.2.4 and 12.2.2.5 are standard of care for transfused DBA subjects who are on chelation medication – which the chronically transfused subjects eligible for this protocol will be receiving; 12.2.2.3, 12.2.2.6 and 12.2.2.7 are extra tests that are specific to the study protocol. The instructions for sample collection and shipping of blood for amino acid levels are delineated in Appendix H. The blood samples will be batched and shipped directly from the participating institution to Case Western Reserve University, Ohio where the tests will be performed. The costs for the mailing will be provided by the Coordinating Center through a FedEx account.

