## Master Protocol

**18.4.2** Is life-threatening (defined as an event in which the subject is at risk of death at the time of SAE; this does not refer to an event which hypothetically might have caused death if more severe)

**18.4.3** Requires inpatient hospitalization or prolongation of existing hospitalization

**18.4.4** Results in more frequent need for erythrocyte transfusions (more than pre-study)

**18.4.5** Results in persistence or significant disability or incapacity

**18.4.6** Results in overdose (defined as the intentional or accidental ingestion of study drug at any dose which is considered medically relevant and excessive)

**18.4.7** Is medically significant (defined as the event may jeopardize the subject and may require medical or surgical intervention to prevent one of the outcomes listed above)

**18.4.8** Any SAE occurring after the subject has signed the informed consent form, and until 12 weeks after the subject has stopped study participation, must be reported.

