### 18.5 Assessment Terms for SAE and Causal Relationship to Study Drug

**18.5.1 DEFINITE** means there is a reasonable causal relationship between study drug and the SAE. The event responds to withdrawal of drug and recurs with re-administration of the study drug (if clinically feasible).

**18.5.2 PROBABLE** means there is a reasonable causal relationship between study drug and the SAE. The SAE tapers or diminishes once study drug has been discontinued. Re-administration of the study drug not required. Relationship between study drug and SAE cannot be reasonably explained by the known characteristics of subject's clinical state.

**18.5.3 POSSIBLE** means there is a reasonable causal relationship between study drug and the SAE but the SAE could have been produced by subject's clinical state or by other means of treatment or medications concurrently administered to the subject.

**18.5.4 UNLIKELY** means there is a temporal relationship to study drug administration but no reasonable causal relationship exists between study drug and SAE. The SAE does not follow a reasonable sequence from administration of study drug. SAE could have been produced by subject's clinical state or by other means of treatment or medications concurrently administered to the subject.

**18.5.5 UNRELATED** means there is no temporal relationship between SAE and study drug administration (e.g., the SAE occurred too early, too late, or study drug not taken) or there is reasonable causal relationship between SAE and another drug, concurrent disease, or circumstance and the SAE. Subjects experiencing AEs that cause an interruption or discontinuation of study drug or those who experience AEs that are present at the end of study should receive appropriate follow-up care. Sites should report the outcome of any AE that caused permanent discontinuation of the study drug or that was present at the end of the study.

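### Involuntary permanent discontinuation of leucine also ends study participation, with no later contact scheduled and no rule for how these subjects enter the 6- and 9-month proportions

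*Combined protocol and SAP*

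**What the plan says.** **Stopping.** Section 13.5.3 has two steps. Any SAE puts leucine on hold until symptoms have gone, and nothing there takes the subject off study. If the SAE is judged possibly related, "the subject will be removed from the study and leucine will be permanently discontinued". Section 15 adds four routes:

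- 15.1, the subject's own choice: "Once off study, subjects will be referred back to his or her referring physician".
- 15.2, PI decision: alternatives are discussed with the subject, "who will then be referred back to his or her referring physician".
- 15.3: "Subjects will be discontinued from study for any Grade III/IV toxicity related to the study drug as determined by PI".
- 15.4: "Subjects will be discontinued from study if non-adherent to protocol".

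**Visits.** Sections 12.2 and 13.3 run from baseline to month 9. Neither has an early-termination or post-treatment visit. Section 12.4 foresees three CRF submissions at three-month spacing, which also ends at month 9.

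**Duties after stopping.** Under 18.4.8, SAEs from consent "until 12 weeks after the subject has stopped study participation, must be reported". Under 18.5.5, "Sites should report the outcome of any AE that caused permanent discontinuation of the study drug", and likewise for any AE present at the end of the study. That section also asks for suitable follow-up care, without a visit or a time.

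**Analysis.** The primary outcome (16.2.1, 16.3) is the response category at 9 months, and also at 6. Section 16.4 promises a proportion and 95% confidence interval for each of CR, PR, NR and progression. Section 16 defines no analysis set and no rule for a missing assessment.

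**Routine data.** Of the tests other than the leucine levels, 12.2.2.7 says "All the others are standard of care for the enrolled subjects". The paragraph that follows names the CBC and reticulocyte count among the standard tests.

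**The concern.** Stopping a drug and leaving a study are different events, and the involuntary rules merge them. A subject taken off leucine at month 4 for toxicity has no 6- or 9-month assessment under the protocol, although the counts and transfusions that define response would normally go on being recorded in a chronically transfused patient.

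All three primary objectives are touched. Efficacy loses outcomes from a group that need not resemble the rest. Safety has reporting duties that outlast the last planned contact. Feasibility depends in part on the non-adherent subjects whom 15.4 removes.

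The link to outcome matters most. If some removals happen because the disease is worsening, the 9-month proportions among those still present will understate Progression and overstate response.

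**Working it through.** **1. The plan's own precision figure (16.5).** Half-width = 1.96 × √(0.5 × 0.5 / 50) = 0.1386, or 13.9 points, giving 36.1% to 63.9%. This agrees with the plan. It presumes that all 50 subjects have an outcome.

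**2. The stopping routes side by side.**

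| Route | Leucine | Participation | Contact scheduled afterwards |
|---|---|---|---|
| SAE hold (13.5.3) | paused | continues | ordinary visits |
| Possibly related SAE (13.5.3) | permanent stop | ends | none |
| Subject's choice (15.1) | stops | ends, voluntarily | none |
| PI decision (15.2) | stops | ends | none |
| Related Grade III/IV toxicity (15.3) | stops | ends | none |
| Non-adherence (15.4) | stops | ends | none |

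No section describes a subject who is permanently off leucine but still followed.

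**3. The link to outcome.** Section 18.4.4 makes a need for more frequent transfusion than before the study an SAE. Section 16.3 d uses more frequent transfusion to define Progression. Section 13.5.3 removes a subject whose SAE is possibly related. Together, a progressing subject whose event is judged possibly related leaves before the 9-month assessment that would record the progression.

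**4. The denominator.** The documents give no dropout rate, so I assume 5, 10 or 15 of 50 stop early and hold the rate among those evaluated at 20%.

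| Stop early | Responders / evaluated | Responders / all 50 | Half-width at p = 0.5, evaluated only |
|---|---|---|---|
| 5 | 9/45 = 20% | 9/50 = 18% | 14.6 points |
| 10 | 8/40 = 20% | 8/50 = 16% | 15.5 points |
| 15 | 7/35 = 20% | 7/50 = 14% | 16.6 points |

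The plan does not say which denominator applies. The choice moves the response rate by 2 to 6 points. The loss of precision is 0.7 to 2.7 points against 13.9.

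**5. Progression.** Each unobserved subject carries 1/50 = 2 points. With 10 stoppers the 9-month Progression proportion is undetermined by up to 10 × 2 = 20 points. CRF entries made before the stop may narrow this, but no rule says that they count.

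**6. The safety window.** For a completer whose participation ends at month 9, the period from first dose to the end of SAE reporting is about 39 + 12 = 51 weeks. The last 12 weeks (12/51 = 24%) have no scheduled contact. For an early stopper the same 12 weeks follow the stop.

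**The case against.** The other side has real points, and several limit the claim.

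- A reader might infer that every stopping rule ends participation. That is not so: the SAE hold stops only the drug, and 15.1 is genuine voluntary withdrawal.
- A reader might infer that subjects who stop have no outcome data at all. Monthly CRF data exist up to the stop, and a subject who stops after month 6 has a 6-month assessment.
- A reader might add all 10 stoppers to the responders and put the possible rate at 18/50 = 36%. That bound is not credible. Section 14.1 assesses response at 6 and 9 months of treatment, so a response that begins off leucine would not be credited to it. One already present at the stop is on the monthly CRF.
- A reader might infer that sites have no contact, or are told not to collect data. No section says so. Section 18.1 accepts events that the subject volunteers, 18.5.5 asks for follow-up care, and transfused patients attend often. What is missing is a scheduled contact, a time and a responsible party.
- Removals under 15.2 and 15.4 need not track a bad course. The outcome link is shown only for the possibly related SAE route.

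It can also be argued that the NR definition in 16.3 c already absorbs stoppers, since it includes any response short of PR or CR. That wording concerns an observed response and does not mention a missing one. Counting stoppers as NR would settle the response denominator, but could place progressing subjects in the wrong category.

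Finally, Section 8 gives a total length of 12 to 15 months, which leaves 3 to 6 months beyond the 9 months of leucine. No visit is assigned to that time, and Section 16 places the end of the study at 9 months. The CRF and SAE form (Appendices G and I) are not in the public text, so an off-study page there cannot be excluded.

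**Conclusion.** The concern holds for involuntary permanent discontinuation: a possibly related SAE under 13.5.3, and Sections 15.2, 15.3 and 15.4. For these subjects the plan provides no 9-month response, and no 6-month response if they stop earlier. It gives no rule for the denominator. The gap in scheduled contact for 18.4.8 and 18.5.5 affects completers as well as early stoppers.

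On assumed losses of 5 to 15 subjects, the efficacy effect is modest for response (2 to 6 points, depending on the denominator) and potentially larger for Progression (20 points at most with 10 stoppers). Both sizes rest on assumed dropout. The textual finding does not, apart from what the unseen appendices may contain.

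This is a descriptive pilot with a convenience sample, so no test or power claim is affected. The amendment is still worth making: removal can depend on the primary outcome, and an analysis rule alone can fix the denominator but cannot supply the unobserved course.

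**What to change.** Reconcile 13.5.3, 15.2 to 15.4, 18.4.8, 18.5.5 and the 13.3 schedule, leaving the criteria for stopping leucine as they are.

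1. Define off study drug and off study separately, and reserve the second for withdrawal of consent.
2. For subjects off drug, record CBC, reticulocytes, transfusions and the start of any other DBA therapy at months 6 and 9, from routine visits or the treating hematologist's records.
3. State in 16.4 that all proportions are reported over all enrolled subjects who started leucine. Do not credit a response that begins after leucine stops or after other DBA therapy starts. Count progression seen up to the stop.
4. Add an early-termination CRF page, unless Appendix G already has one.
5. Add one telephone or chart contact at the end of the 12-week SAE window for every subject, and name who is responsible for it.

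The cost is a protocol amendment, possibly one CRF page, one contact per subject, and consent wording that permits record follow-up after leucine stops. The CBC and reticulocyte counts are already standard of care, so no new tests are needed.
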